The present study will be a single site, prospective, single arm observational study of minimal risk consisting of at least 200 participants who suffer from cold symptoms. The participants must meet additional inclusion/exclusion criteria (see Inclusion/Exclusion Criteria). Participants will begin taking the powder drink-mix at the onset of their cold symptoms. Onset is defined as the point in time the participant experiences 2 or more cold symptoms (cough, hoarseness, muscle ache, nasal drainage,

nasal congestion, scratchy throat, sore throat, sneezing, or an oral temperature greater than 37.7 °C (99.9 °F)). When the participant experiences 2 or more symptoms, they will report symptoms in the cold start form. If they meet the criteria for a cold, they will start completing the daily cold symptom diary prior to taking the test product. After consuming the product, the participant will complete the cold symptom diary daily until all symptoms resolve. Since none of the ingredients in the test product have been seen to provide relief from fever or pain, the participant will be allowed to take a pain reliever and fever reducer (e.g. ibuprofen or acetaminophen). If medication is taken, the participant will record this in their symptom diary.

Study enrollment and management will be decentralized, where participants do not visit an investigator or a clinic for clinical assessment. The participants will participate in the study at home. All data collected from during this study will be reported by the participant via eCRFs, eDiary, and other electronic data entries. If a visit is required, it will be conducted via remote contact by telephone.

4.1.Test Product

Overview:

Participants in this study will consume the test product twice a day (4-6 hours apart) at the onset of cold symptoms. The participant will mix one packet of the test product in 6-8 ounces of water. The test product will be delivered to the participants' residence in a single shipment consisting of an18-day supply (36 packets) of the test product. The study participant will mix the contents of the packet into 6-8 oz. of hot water and drink twice a day during the duration of the cold.

Below is the description of the test product and its ingredients.

Test Product

Description: Combining whole food sourced Vitamin C, Echinacea, Ivy Extract, Zinc, Ginger and Turmeric. This formula is designed to support the immune system while reducing the duration of cold.

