- At time of enrollment, participant will be given access to the HIPAA compliant study portal.
 - The study portal provides access to study information, signed informed consent form, instructions for product use, frequently asked questions, study surveys, symptom diary, and data collection tools.
- Participant shall complete baseline assessments upon access to the portal.
 - Baseline assessment will include questions regarding the participants' demographics, medications, detailed information regarding previous colds, including treatment.
- To ensure that baseline assessments are completed before test product is used by the
 participant, study materials and study welcome package will be shipped to the participant once
 the clinical study manager/clinical operations coordinator confirms that the baseline assessment
 has been completed.
- The welcome package will include an information sheet that will outline instructions for their participation in the trial, the test product, disposable thermometer, and paper forms of the

- documents (paper form of study documents will be provided for real time data collection, in the event that the participant cannot log into the study portal to input data).
- Once the participant receives the test product, the participant will log into the study portal to acknowledge the receipt of the test product.
- Study start date will be the date of acknowledgement of receipt of test product.
- Participant will be sent weekly email reminders that remind them of their participation in the study. Once the participant indicates they are experiencing a cold. The participant will be reminded by email daily to complete their symptom diary.
- At the onset of their cold symptoms, the participant will complete the cold start form.
 - Onset is defined as the point in time the participant experiences 2 or more cold symptoms (cough, hoarseness, muscle ache, nasal drainage, scratchy throat, sore throat, sneezing, oral temperature greater than 37.7°C (99.9 °F)).
 - If fever is a symptom that the participant experiences, they will use the provided disposable thermometer to take their temperature and record it in the diary.
- If the participant meets all the criteria for a cold, they will start their symptom diary prior to taking the test product.
- After completing the surveys, the participant will take the test product. The participant will mix 1 drink-mix packet into 6-8 oz of water and consume the whole drink.

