7.1. Study Outcomes Measures

Analysis populations:

The *intent to treat* (ITT) population consists of all participants who are consented, report the onset of cold symptoms, and have taken the test product at least once. The primary analysis will be in the ITT population.

Primary Endpoint:

• The primary endpoint will be time to freedom from cold symptoms, with the clock starting at the onset of the cold. Where the onset is defined as the point in time when the participant experiences 2 or more cold symptoms. The primary analysis will be a Kaplan-Meier analysis of time to absence of all symptoms, based on the participant's self-report. There is no control group for the primary analysis.

Secondary Endpoints:

- Secondary endpoints involve the duration and severity of the separate cold symptoms.
- Comparison against the participant's normal behavior.
- Net Promoter Score.
- Adverse events will be summarized.
- An additional data presentation will consist of results from both Treatment and Control in similar studies appearing in the literature. There will be no formal statistical comparison of results from this study and historical studies.

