13.1.4. Appendix D Baseline Form

Baseline

- 1. Demographics
 - a. Race/Ethnicity (Black or African American, White, Asian, American Indian or Alaska Native, Native Hawaiian or another pacific islander, other: _____, do not want to share)
 - b. Sex (M, F, or Do not want to share)
- 2. On average how many colds do you get a year?
- 3. On average How long do your colds usually last? (1-3 days, 4-6 days, 7-9 days, >10 days)
- 4. When you have a cold what Cold Symptoms do you usually experience? (check all that apply)
 - a. Cough
 - b. Hoarseness
 - c. Muscle aches
 - d. Runny Nose
 - e. Nasal Congestion
 - f. Scratchy Throat
 - g. Sore throat
 - h. Sneezing
 - i. Oral Temp > than 37.7 °C (99.9 °F)
 - j. Other:
- 5. Do you take any medication when you have a cold (i.e. Dayquil/Nyquil, Advil, or Prescription etc.)?
 - a. If so, which medications do you take?
 - b. How often do you normally take them? (once a day, as needed, or as instructed)
 - c. Are they successful in treating your symptoms?
- 6. Do you take any supplements when you have a cold (Emergen-C, Vitamin C, Airborne, Nettipot, etc.)?
 - a. If so, which supplements do you take?
 - b. How often do you take the supplement when you have a cold? (once a day, several times a day, every other day, once in a while)
 - c. Are they successful in helping with your symptoms?

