13.1.5. Appendix E Symptom Diary

Daily Symptom Survey

BEFOREtaking the test product OR any allowed medication, please answer all of the following questions daily for the duration of your cold symptoms.

REMINDER: DURING THE TRIAL, YOU ARE NOT ALLOWED TO TAKE ANY COLD MEDICATIONS (NYQUIL/DAYQUIL, TYLENOL COLD, COUGH SYRUP/LOZENGES, ETC.)

1. Cough			
0	1	2	3
No Symptom	Slight	Moderate	Severe
2. Hoarseness			
0	1	2	3
No Symptom	Slight	Moderate	Severe
3. Muscle aches			
0	1	2	3
No Symptom	Slight	Moderate	Severe
4. Runny Nose			
0	1	2	3
No Symptom	Slight	Moderate	Severe
5. Nasal Congestion			
0	1	2	3
No Symptom	Slight	Moderate	Severe
6. Scratchy Throat			
0	1	2	3
No Symptom	Slight	Moderate	Severe

7. Sore throat

0	1	2	3
No Symptom	Slight	Moderate	Severe
8. Sneezing			
0	1	2	3
No Symptom	Slight	Moderate	Severe

- 9. Did you take any pain/fever reducer (ibuprofen/acetaminophen today? (Y/N)
 - a. Why?
 - b. Did it work? (Y/N)
- 10. Have you taken any other cold medications (Nyquil, Dayquil, other cold medication, cough drop, cough syrup, etc.)? (Y/N)
 - a. If yes, please exit from the study
- 11. Have you seen a doctor for your symptoms? (Y/N)
 - a. If yes, were you prescribed anything? $(Y/N) \rightarrow$ if yes please exit from the study
- 12. Did you experience any side effects after taking the product? (Y/N)
 - a. If yes, please fill out the Adverse Event form.

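### The symptom lists behind the primary endpoint do not match: section 6.1 drops nasal congestion from the onset rule, and fever counts towards onset but has no item in the diary shown

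*Combined protocol and SAP*

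**What the plan says.** **Start of the clock.** Onset is two or more symptoms. Section 4 (Study Design) lists nine, the last five being "nasal congestion, scratchy throat, sore throat, sneezing, or an oral temperature greater than 37.7 °C (99.9 °F". Section 6.1 (Study Procedures) restates the rule, but its list runs "nasal drainage, scratchy throat, sore throat, sneezing, oral temperature greater than 37.7°C", with no nasal congestion.

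**Fever.** Both lists include it. For a participant with fever, section 6.1 adds that "they will use the provided disposable thermometer to take their temperature and record it in the diary", without giving a frequency. The baseline form (Appendix D, item 4) also treats it as a cold symptom, "Oral Temp > than 37.7 °C (99.9 °F", and lists congestion too.

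**Diary.** Section 4 says that "the participant will complete the cold symptom diary daily until all symptoms resolve". The diary (Appendix E) instructs: "please answer all of the following questions daily for the duration of your cold symptoms". Its items run from 1 to 12 without a gap. Items 1 to 8 are symptoms scored 0 to 3, and item 5 is nasal congestion. None is fever or temperature. The nearest is item 9, "Did you take any pain/fever reducer (ibuprofen/acetaminophen today? (Y/N", with follow-ups on the reason (9a) and on whether it worked (9b). Items 10 to 12 cover other cold medication, doctor visits and side effects.

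**Event.** The synopsis and sections 3, 4.4 and 7.1 agree: "The primary analysis will be a Kaplan-Meier analysis of time to absence of all symptoms", based on self-report. Section 7.3 adds a Kaplan-Meier median time to resolution for each individual symptom. It leaves further detail to a SAP still to be written.

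**The concern.** The start and the end of the only primary analysis rest on different symptom sets. Under section 6.1 congestion cannot help to start the clock, yet the diary scores it to its end. Fever can start the clock under either section, yet the diary shown does not follow it to its end.

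Three things are at stake. Two sections in force give different time zeros for some participants, and so different membership of the ITT population, which section 7.1 ties to reporting onset and taking the product at least once. A participant whose fever outlasts the other symptoms could be recorded as resolved too early. And the planned per-symptom median cannot be produced for fever from the diary shown.

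**Working it through.** **1. The plan's own figure.** Section 7.2 expects 40% of 200 enrolled participants to have a cold: 200 × 0.40 = 80. This matches the desired 80 treated participants in section 5.1. The figure reproduces and is not in dispute; it is used only for scale in step 5.

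**2. The lists side by side.** Nasal drainage and runny nose are taken as the same symptom.

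| Symptom | Section 4 onset | Section 6.1 onset | Appendix E diary |
|---|---|---|---|
| Seven shared: sore throat, scratchy throat, sneezing, cough, hoarseness, muscle aches, runny nose | yes | yes | yes |
| Nasal congestion | yes | no | yes |
| Oral temperature above 37.7 °C | yes | yes | no |
| Total | 9 | 8 | 8 |

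Section 4 names drainage and congestion separately, so congestion cannot be read into drainage in section 6.1.

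**3. Who the onset conflict touches.** Under section 4 there are 9 × 8 / 2 = 36 qualifying pairs of symptoms; under section 6.1 there are 8 × 7 / 2 = 28. The 36 − 28 = 8 pairs that differ are congestion plus one other symptom. Anyone with congestion and at least two others qualifies under both rules. The conflict is therefore confined to participants with congestion and exactly one other listed symptom. These are counts of possible pairs, not of participants.

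**4. Where resolution of fever could be read.** Five forms are shown (Appendices C to G).
- Screening asks only about comfort with taking one's own temperature.
- Baseline asks about usual colds.
- The diary has items 9a and 9b only, which reach only users of a reducer and hold no temperature.
- The exit form asks about experience, perceived help and recommendation.
- The adverse event form asks about side effects.

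None records a statement or date of resolution. The exit form is prompted both at resolution and at day 18, so its completion does not identify the event. Stopping the diary does not either, since section 7.3 uses the last report as a censoring date. On the forms shown, the event has to be derived from diary items, and fever has none.

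**5. Effect on the curve.**
- *Shifted event time.* With 80 treated participants and no earlier censoring, each contributes 1/80 = 1.25 percentage points, and only between the two possible times. If, as an assumption, 10% or 20% had already been censored, 1/(80 × 0.9) = 1.39 and 1/(80 × 0.8) = 1.56 points.
- *Participant left out of the ITT population.* Let k of the other 79 be resolved on a given day, with no censoring. The resolved share is k/79 without this participant. With the participant it is k/80 if still ill, a difference of k/(79 × 80), or (k + 1)/80 if resolved, a difference of (79 − k)/(79 × 80). Either is at most 1/80 = 1.25 points, but it can arise on any day.

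**6. Direction.** With the resolution time held fixed, an early event (fever) and a late time zero (congestion) both shorten recorded duration. But onset also triggers product start, and under the trial's own hypothesis a later start could change when the cold resolves.

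**The case against.** The strongest reply is that the endpoint is self-reported: a participant who still has fever is told to keep the diary going, and section 6.1 orders the temperature to be recorded. Section 4 also allows for other electronic entries beyond the diary. On this view Appendix E is simply a form that lags the protocol. Part of this stands. A reader might infer that temperatures were never collected; the documents do not show that, only that the form shown has no place for them. The missing temperature row in the section 6.2 schedule proves little either, because a diary temperature would fall under the diary row. But the self-report has to be captured somewhere, and no form shown asks for it directly.

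Items 9a and 9b are more than nothing: a participant may give fever as the reason for a reducer and say whether it worked. They remain indirect and miss untreated fever.

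On congestion, section 4, the baseline form and the diary agree and only section 6.1 differs, which looks like a transcription slip. That is plausible. The cold start form, which applies the rule, is not in the text supplied, and some pages were removed before review. If that form follows section 4, the onset conflict is one of wording only.

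Finally, the trial has no control arm and plans no formal comparison with historical results, so no test depends on this. That limits the weight of the point but does not remove it, because the estimated duration is the main result.

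**Conclusion.** The mismatch is real and should be corrected. Sections 4 and 6.1 contradict each other on nasal congestion. Section 6.1 sends temperature to a diary that, as shown, has no field for it. On the forms shown, freedom from fever cannot be verified, and a per-symptom median is possible for eight of the nine symptoms in section 4.

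The number of participants affected cannot be derived, because the documents give no frequencies for fever or congestion; they support neither a small nor a large overall effect. Per participant, the scale is 1.25 percentage points, assuming 80 treated and no earlier censoring. For a shifted event time this applies between the two times. For a participant left out of the ITT population it is an upper limit that can apply on any day.

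A reader might infer that both gaps bias the trial towards a shorter cold. That follows only if resolution time is unaffected by when the product is started, so no firm overall direction is claimed. Whether the onset conflict affects the data at all depends on the cold start form.

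**What to change.** 1. Reconcile section 4, section 6.1, the cold start form and the diary to one symptom list. Onset also triggers product start, so which onset list applies is for the sponsor and investigator to decide.
2. Then choose one of two routes. Either add a temperature or fever item to the diary, completed until resolution by participants who report fever, after confirming that the supplied disposable thermometer allows repeat readings. Or restate the primary endpoint in the synopsis and sections 3, 4.4 and 7.1 as freedom from the eight symptoms that the diary scores.
3. State in the protocol and SAP that the event is the first diary day on which every listed item is scored 0 (and fever is absent, if it is kept).

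The SAP alone can settle a rule, but it cannot supply readings if none were taken, so the form needs attention before data collection. The cost is a wording change in sections 4 and 6.1, a check of the cold start form, one sentence on the event, and either one diary item or edits to the four endpoint statements. The downside is one short extra diary entry for participants with fever, or a slightly narrower endpoint.

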2.2.3. Minimization of Risks

Research participants will be carefully screened to meet enrollment criteria. Participants meeting exclusion criteria will not be enrolled. The study participant informed consent will be presented with clear description of the study requirements and opportunity to have questions answered before enrollment will be provided. Once an event occurs, review of symptoms will be

ascertained daily until symptoms have resolved or for 18 days. Reporting of adverse events will be reviewed routinely and in accordance with regulatory guidelines (21CFR, GCP) by the Principal Investigator. Participants with occurrence of worsening symptoms or adverse events will be advised to stop the product and may seek medical attention and exit the study.

3. Study Objectives

The purpose of the present study is to evaluate 1) the impact of the Immune Support test product on the duration of symptoms of the common cold in adult participants and 2) the subjective experience of these participants related to general health, common cold symptoms, and personal experience with the product. [13, 18, 29, 32]

This will be evaluated based on the primary and secondary endpoints. These endpoints, the analysis populations, and their respective measures are described below. Further details on the methods for measuring the outcomes can be found in the Study Outcome Measures and Analysis Plan sections.

Primary Endpoint:

The primary endpoint will be time to freedom from cold symptoms, with the clock starting at the onset of the cold. Where the onset is defined as the point in time when the participant experiences 2 or more cold symptoms. The primary analysis will be a Kaplan-Meier analysis of time to absence of all symptoms, based on the participants' self-report. There is no control group for the primary analysis. [5]

Secondary Endpoint:

- Secondary endpoints involve the duration and severity of the separate cold symptoms.
- Comparison against the participant's normal behavior.
- Net Promoter Score.
- Adverse events will be summarized.
- An additional data presentation will consist of results from both Treatment and Control in similar studies appearing in the literature. There will be no formal statistical comparison of results from this study and historical studies.

4.Study Design

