- Participant will take the test product twice a day, at least 4-6 hours apart.
- The next day the participant will complete their symptom diary prior to taking the test product. Once completed they will mix 1 packet of the test product into 6-8 oz of water and consume the whole drink. They will take the test product again 4-6 hours later.
- The participant will complete this process daily until their cold symptoms resolve or for 18 days, whichever is shorter.
- If the participant takes ibuprofen or acetaminophen at any time, the participant will record this on their symptom diary.
- After taking the test product, the participant will be instructed to fill out an Adverse Event form for any side-effects experienced.
- The participant will be prompted, by email, to complete the study exit form once the participant's symptoms resolve completely or after 18 days, whichever is shorter.
- Neither the sponsor nor Hawthorne Effect, Inc. will make any attempt to collect any unused test product.
- Upon receipt of study exit survey and review of completed study forms, participant will receive an Amazon gift card of \$25 via email.

6.2.Study Schedule of Activities

Assessments	Screening	Consent	Before Receipt of Test Product	Product Received	Event Start Date**	Days 1-18*	Study Exit***
Study Window							
Screening Survey	Х						
Consent		Х					
Baseline Survey			х				
Demographics			х				
Acknowledgement of Receipt of Test Product				Х			
Test Product Consumed****					Х	Х	
Symptom Diary					Х	Х	Х
Meds & Supplements			Х				
AE Assessment					Х	Х	Х
Study Exit Survey							Х

^{*}Participant will participate in the study starting on the day of the cold until the cold symptoms resolve or 18 days whichever is shorter.

^{**} The day the participant experiences 2 or more of the protocol defined symptoms

^{***} The participant will exit the study at the time of complete cold symptom resolution, 18 days after the start of cold symptoms, or at 90 days if no cold is experienced by the participant.

^{****} The product will be consumed twice a day, 4-6 hours apart

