6.4.3. Serious Adverse Events

A Serious Adverse Event is an Adverse Event that leads to death or to serious deterioration in the health of the participant that either resulted in a life-threatening illness or injury, or a permanent impairment of a body structure or body function.

6.5.Lost to Follow-Up

If a participant fails to provide event information via the study/patient portal 30 days after the start of the trial, the remote coordinator will attempt to contact the participant to ascertain whether or not the participant has had a cold or not and if the participant wishes to and/or should continue in the study.

Before a participant is deemed lost to follow up, the investigator or designee must make every effort to regain contact with the participant (where possible, 3 telephone calls and, if necessary, a certified letter to the participant's last known mailing address or local equivalent methods). These contact attempts should be documented in the participant's study record.

Should the participant continue to be unreachable, he/she will be considered to have withdrawn from the study and the study exit form will be completed.

6.6.Test Product Packaging/Handling/Storage/Accountability

- The 18-day supply of test product (36 packets) will be packaged and labeled with a study ID number.
- Participants will receive guidance on how to report receipt, store, and use the test product.
- Hawthorne Effect Inc. will support storage and shipment of test product, documentation of test product assignment, and completion of test product accountability.

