13.1.6. Appendix F Study Exit Form

Study Exit

1	1. Please rate your overall experience with the test product.										
Poo		1	2	3	4	5 Neutral	6	7	8	9	10 Excellent
1	a. W	/hy? (1	ree re	sponse)							
2. Do you feel that the test product helped with your cold?											
Not a		1	2	3	4	5 Neutral	6	7	8	9	10 definitely
3. How likely are you to recommend the test product to your friends or family members?											
Not 1		1 ly	2	3	4	5 Neutral	6	7	8	9	10 Extremely Likely
4. Do you feel that the test product helped your body cope with the elements?											
Not a		1	2	3	4	5 Neutral	6	7	8	9	10 definitely

5. Is there anything else that you would like to let us know about your experience with the product (taste, smell, consistency, or other)? $(y/n) \rightarrow$ (free response)

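### No exit-form prompt is specified for treated participants who leave early, so the Net Promoter Score, collected only on that form, is at risk of bias, probably upward

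*Combined protocol and SAP*

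**What the plan says.** Sections 3 and 7.1 list the "Net Promoter Score" among the secondary endpoints. The item behind it is question 3 of the Study Exit form in Appendix F: "How likely are you to recommend the test product to your friends or family members". No other form in the appendices carries it.

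Section 6.1 has one scheduled trigger for that form. Participants are "prompted, by email, to complete the study exit form once the participant's symptoms resolve completely or after 18 days", whichever comes first. The schedule in Section 6.2 places the Study Exit Survey in the Study Exit column, and the footnote to that column says that participants "exit the study at the time of complete cold symptom resolution, 18 days after the start of cold symptoms, or at 90 days" where no cold has occurred.

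The protocol creates other exits:
- Section 4.2 exits anyone who takes another cold remedy and withdraws anyone prescribed an antibiotic or other medication.
- Diary items 10 and 11 (Appendix E) tell such participants to leave, without pointing them to a form.
- Section 2.2.3 says that participants with worsening symptoms or adverse events "will be advised to stop the product and may seek medical attention and exit the study".

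Section 6.5 covers people who cannot be reached: "he/she will be considered to have withdrawn from the study and the study exit form will be completed".

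Section 7.3 sets censoring rules for the time-to-event analysis. It gives no population, scoring rule or missing-data rule for the Net Promoter Score.

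**The concern.** A satisfaction score describes users only if the users who gave up on the product are asked as well. Taking another remedy, or leaving because of worsening or a side effect, is plausibly linked to a poor opinion of the product. If the form is sent just as Section 6.1 states, these people receive no scheduled request, and their ratings can be missing for reasons related to what the rating measures.

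At stake is a descriptive secondary endpoint and the other product ratings on the same form, in a study whose results Section 10 says will be submitted for publication. A score computed from whoever returned the form would be read as the opinion of everyone treated.

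**Working it through.** **1. Exits set against triggers.**

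| Way out of the study | Section 6.1 prompt | Section 6.2 footnote |
|---|---|---|
| All symptoms resolved | yes | yes |
| Day 18, still symptomatic | yes | yes |
| Day 90, no cold | no | yes |
| Other cold remedy (4.2; diary item 10) | no | no |
| Prescription (4.2; diary item 11) | no | no |
| Worsening or adverse event, participant chooses to exit (2.2.3) | no | no |
| Unreachable (6.5) | no | no; 6.5 has the form completed, respondent not named |

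The three exits for another remedy, a prescription, or worsening or an adverse event appear in neither place. Diary item 12 does send the participant to a named form (the adverse event form), so the diary can do this; items 10 and 11 do not.

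**2. The plan's own figure.** Section 7.2 expects 40% of 200 enrolled to have a cold: 200 × 0.40 = 80, which reproduces. I use 80 as the expected number treated. The footnote also puts the other 200 − 80 = 120, who would have had no cold and so no reason to use the product, into the Study Exit column. With no stated population for the score, it is unclear whether they count.

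**3. Formula.** Take the score as the percentage of promoters minus the percentage of detractors, from −100 to +100 (an assumption, since the protocol gives no scoring rule). Let d be the share of treated participants who leave early. Suppose that all prompted participants answer and no early leaver does.

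- Score in all treated = (1 − d) × S(prompted) + d × S(leavers)
- Bias of the reported score = d × [S(prompted) − S(leavers)]

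**4. Numbers.** The documents give no early-exit rate and no scores, so every input here is assumed. With S(prompted) = 30, the bias in points is:

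| d (of 80) | leavers 50 | leavers 30 | leavers 0 | leavers −30 | leavers −60 |
|---|---|---|---|---|---|
| 5% (4) | −1 | 0 | 1.5 | 3 | 4.5 |
| 10% (8) | −2 | 0 | 3 | 6 | 9 |
| 20% (16) | −4 | 0 | 6 | 12 | 18 |
| 30% (24) | −6 | 0 | 9 | 18 | 27 |

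Example: at d = 20% with leavers at −30, the score in all treated is 0.8 × 30 + 0.2 × (−30) = 18, and the bias is 30 − 18 = 12.

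**5. Bounds without a guess at the leavers' scores.** Put all leavers at −100, then at +100: 30(1 − d) ± 100d. This gives 23.5 to 33.5 at 5%, 17 to 37 at 10%, 4 to 44 at 20%, and −9 to 51 at 30%.

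**6. For scale.** With 50% promoters and 20% detractors (assumed, score 30) and n = 80, the 95% half-width is 1.96 × 100 × √[(0.5 + 0.2 − 0.3²)/80] = 17.1 points. The larger biases in the table match or exceed this sampling error; the smaller ones are well inside it.

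**The case against.** The strongest reply is that the text is silent here and does not exclude early leavers. Section 6.1 describes one email and does not call it the only route. The Study Exit column could be read as covering anyone who exits. Section 6.3 lets a coordinator prompt for incomplete forms, the gift card in Section 6.1 depends on the exit survey with no stated exclusion of early leavers, and every participant has portal access to the surveys. This stands to the extent that one cannot say early leavers will go unprompted, only that no prompt is specified for them. It does not close the gap. The coordinator's prompt is discretionary, the gift card does not cause a form to be sent, and an unreachable person cannot supply a rating.

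A reader might infer that the score is biased upward as a matter of fact. The documents do not support that. Section 4.2 withdraws people for prescriptions given for any reason, including reasons unrelated to the product. Stopping the product is not the same as leaving: Section 2.2.3 makes exit optional, and Section 6.4 speaks of stopping and seeking medical attention without mentioning exit, so some who stop will still reach a scheduled prompt. The day-18 trigger also reaches people who have not recovered and who may rate the product poorly.

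A reader might also infer that adverse events are lost for early leavers. That loss is largely covered: diary item 12 and the adverse event form operate daily, and Appendix F contains no adverse event question.

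Finally, Section 7.3 defers detail to a later SAP. A denominator and a missing-data rule could be set there, but an analysis plan cannot recover ratings that were never requested.

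**Conclusion.** The concern holds as a gap in data collection. For treated participants who leave early, no exit-form prompt is specified, and no population or missing-data rule is given for the score. The Net Promoter Score is therefore at risk of bias, probably upward, because those who turn to another remedy or leave for a side effect plausibly rate the product lower.

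Neither the size nor the sign can be derived from the documents. The range of −6 to +27 points rests on the assumed score of 30, the assumed exit shares and leaver scores, and complete response among those prompted. The bias is zero if leavers rate the product as others do. The endpoint is secondary and descriptive, and the primary Kaplan-Meier analysis does not use it. The change is still worth making, because it is cheap and must be in place before participants begin to leave.

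**What to change.** - **Section 6.1 and the Study Exit footnote in Section 6.2:** trigger the exit form at every exit after the first dose, including exits through diary items 10 and 11 and any withdrawal. Participants who exit through those items while in the portal can be shown the form at once.
- **Section 7 or the SAP:** name all treated participants as the target population for the Net Promoter Score and state the scoring rule. Report the response rate by exit reason, with the bounding analysis in step 5 applied to the missing ratings.
- **Section 6.5:** for unreachable participants, state that only an administrative record of exit date and reason is completed, and that the participant-rated items are left missing. Appendix F has no field for date or reason, so this needs a short separate record.

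The cost is one portal trigger, a short record and a few sentences. The downside is a few more reminder emails and a possibly less favourable score.
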